7. STUDY DESIGN

7.1. Study Overview

This is a natural history cohort study evaluating patterns of brain inflammation and its relationship to qualifiers of stroke severity, functional outcome and stroke location.

Patients participating in this study will be required to undergo physical examination, blood testing and PET-MRI imaging acquisition at distinct time points.

7.2. Participation in this study will not influence the patients' ability to receive standard of care treatment for stroke, as deemed necessary by the treating physician. Overall Study Duration and Follow-Up

The study period will consist of screening and two time point PET and MRI assessments during an approximately 90-day follow-up period. The end of study is defined as final collection of data.

7.3. Early Termination of Study

The Sponsor-Investigator, after consultation with Biogen, may terminate this study at any time.

7.4 Participant Identification and Recruitment

Study Investigators who are members of the direct care team looking after the patient on the stroke ward, will identify them as potentially eligible. They will be approached by the Investigator and will have the study explained to them and be given a participant information sheet to read and consider. If they decide to take part after having any questions answered, the Investigator will take written informed consent before the patient has their screening visit.

8. STUDY POPULATION

8.1. Inclusion Criteria

To be eligible to participate in this study, candidates must meet the following inclusion criteria at screening:

- 1. Able to understand the purpose and risks of the study and provide signed and dated informed consent and authorization to use protected health information in accordance with national and local subject privacy regulations in accordance with all local and national regulations OR according to the local institutional review board's (IRB's)/ethics committee's (EC's) guidelines OR by another process compliant with applicable national laws and regulations and IRB/EC requirement
- 2. Aged 18-85 years of age at the time of informed consent
- 3. Clinical diagnosis of supratentorial acute ischemic stroke within the previous 10 days. Note: An acute brain CT or MRI scan must be available from the patient's history to assess eligibility for the study and be consistent with the diagnosis of acute ischemic stroke.
- 4. Score of at least 5 points on the NIHSS at Screening.
- 5. Subjects of childbearing potential (male and female) must be willing and able to practice effective contraception during the study and for 4 weeks after their Day 90 appointment.
- 6. Negative serum/ urine pregnancy test on all females of childbearing potential within 2 days before each PET study.

8.2. Exclusion Criteria:

Candidates will be excluded if any of the following exclusion criteria exist at screening, or at the time point specified in the individual criterion listed:

- 1. Unable or unwilling to provide informed consent.
- 2. Presence of acute intracranial hemorrhage on acute brain CT or MRI
- 3. Inability to comply with study requirements (including implanted pacemaker).
- 4. Subject has contraindications to undergoing MRI examination (including, but not limited to metal foreign bodies incompatible with MRI exposure, cardiac pacemakers, renal impairment that contraindicates gadolinium etc.) or PET scan.
- 5. Subject has participated in a research and/or medical protocol involving nuclear medicine, PET or radiological investigations with radiation exposure that, when combined with the radiation exposure from the present study, would exceed 10 mSV in addition to the natural background radiation, in the previous 12 months.
- 6. Other unspecified reasons that, in the opinion of the Investigator make the subject unsuitable for enrollment.
- 7. Nursing or pregnant females or females planning to become pregnant during study participation.
- 8. Claustrophobic, unable to hold head continuously still for 90 minutes, or unwilling to undergo PET or MRI imaging and related procedures required for this study.

9. Genetic polymorphism consistent with low TSPO binding affinity (expected in 10% of the population).

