3. SYNOPSIS

Tracking Number: GBR-TYS-16-11060

Protocol Title: TSPO PET as a measure of post-stroke brain inflammation:

a natural history cohort

Version Number: 2.0

Name of Study Treatment: Not applicable

Study Indication: AIS

Phase of Development: NA

Rationale for the Study: Stroke is a leading cause of mortality and serious long-term

disability. There is a substantial unmet medical need for new

therapies that can improve outcomes in acute stroke.

Experimental and pathologic data suggest that peri-infarct inflammation contributes to secondary injury after brain ischemia and that blocking inflammation could reduce the volume of brain infarction and improve clinical outcome.

In a recently completed phase 2 placebo-controlled clinical trial, the administration of natalizumab (a potent inhibitor of leukocyte transmigration through the blood –brain barrier [BBB]) in the hyperacute phase of ischemic stroke was associated with beneficial effects in measures of functional outcome, but did not affect the rate of infarct volume growth

during a 90-day assessment period. This apparent

discrepancy between the lack of effect of anti-inflammatory therapy on lesion size and a substantial beneficial effect on functional outcome in ischemic stroke patients has raised

further questions about the manifestation of

neuroinflammation, its pathophysiological role and its relation to patients' functional outcome in stroke patients.

The purpose of this imaging study is to characterize the subacute and longstanding extent of upregulation of the neuroinflammation marker TSPO on glial cells at two time points after stroke. The study will also explore the correlation of TSPO upregulation with measures of stroke

severity and post-stroke functional outcomes.

Study Objectives and Endpoints:

The objectives of this study are:

- To characterize TSPO glial expression in specific regions of interest defined on correlative brain MRI (ROIs; infarct, peri-infarct, thalamus) in the subacute (day 15+7) and chronic (day 90+/-7) phases after an ischemic stroke;
- To determine the magnitude and variability of TSPO uptake at these ROIs during the assessment period;
- To describe changes in TSPO expression between 15 and 90 days
- To explore the relationship between TSPO uptake, blood and infarct volume, and measures of Wallerian degeneration,

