- To characterize post-stroke TSPO glial expression in relation to measures of stroke severity (infarct size, volume and location; NIHSS) and functional outcome (mRS,BI, depression scale, MoCA)
- To characterize post-stroke TSPO glial expression in relation to systemic inflammatory markers in blood

The endpoints that relate to these objectives are:

- PET-derived measures of TSPO radiotracer uptake in the infarct and peri-infarct areas at day 15 and day 90 after a stroke
- PET-derived measures of TSPO radiotracer uptake in ROIs distant from the infarct area (e.g. thalamus, hippocampi, amygdalae and midbrain) at day 15 and day 90 after a stroke
- Correlation of PET-derived measures with clinical and imaging measures of stroke severity (stroke volume, size and NIHSS) and functional outcome (mRS Barthel index, MoCA, depression,) at day 15 and day 90
- Correlation of infarct volume and MRI measures of white matter tract injury determined from DTI MRI with measures of thalamic TSPO uptake (timeactivity curve; measures of mean and max TSPO uptake on summed image sets from TSPO PET
- Correlation of PET derived measures with inflammatory markers in the blood (e.g. cytokines)

Study Design: This is an exploratory, prospective, natural history, imaging

cohort study.

Study Location and Number

of Sites:

The recruiting site will be Imperial College Healthcare NHS

Trust. All study scans will be performed by Imanova,

Hammersmith Hospital

Number of Planned Subjects: Between 15 and 25 subjects, with recruitment ending when

15 participants have completed all study procedures.

Study Population: Subjects aged 18-85 with a supratentorial ischemic stroke of

moderate severity as measured by NIHSS >4 and evidence

of infarction on clinical brain scan at time of stroke:

Duration of Treatment and

Follow-up:

Subjects will participate in this study for approximately 90

days. No treatment will be started as part of the trial

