4. SCHEDULE OF EVENTS

Tests and Assessments	Screening visit ⁹	Day 15 (±3 days)	Day 90 (±7 days)
Eligibility confirmation ¹	X		
Sign Informed Consent Form ²	X		
Demographics and medical history	X		
Physical and neurological examination	X	X	X
Vital signs ³	X	X	X
Height (if available) and weight	X		
Urine (or serum) pregnancy test ⁴	X	X	X
Medications	X		
NIHSS		X	X
mRS		X	X
BI		X	X
Beck Depression Inventory		X	X
Hematology and blood chemistry ^{5,6}	X		
Blood sample for systemic inflammatory profile	X	X	X
Blood sample for TSPO polymorphism genotyping ⁷	X		
Confirmation of genotype eligibility criterion ⁸		X	
PET and MRI scanning		X	X
Adverse Events reporting		throughout	

- 1. All but genotype exclusion criterion, see bullet point 8
- 2. Subjects will be consented prior to screening procedures
- 3. Vital signs include temperature, blood pressure, pulse or heart rate and respiratory rate
- 4. Women with childbearing potential only
- 5. Liver function, renal function and CBC will be performed at screening. Results of tests performed as part of standard of care can be accepted.
- 6. Renal function tests will be repeated before each PET MRI assessment in subjects older than 60 years of age or with known renal impairment
- 7. SNP genotype confirmation is required to determine eligibility. Blood samples for this assessment will be collected at screening only after other eligibility criteria have been met
- 8. Verification of the TSPO SNP genotype exclusion criterion will occur prior to or at the PET MRI acquisition day but will be confirmed before subjects undergo PET-MRI imaging acquisition.

CONFIDENTIAL

The information contained herein may not be used, disclosed, or published without the written consent of the Sponsor-Investigator.

9. Up to 10 days from stroke onset

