9. STUDY PROCEDURES

Once the investigational site has been activated for study participation, subjects may be enrolled if they have met the inclusion criteria in Section 8.1 and have not been excluded based on the exclusion criteria in Section 8.2.

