9.1. Screening, Enrollment and Registration of Subjects

Subjects must provide informed consent before any screening tests or assessments are performed. When the subject signs the Informed Consent Form (ICF), the subject is considered to be enrolled in the study. Subjects will not be eligible for rescreening.

Subjects will be registered at screening visit after the eligibility criteria, with the exception of the TSPO genotype, have been determined.

Subjects will be registered and assigned a unique subject identification number after consent and before undergoing imaging acquisition. Any subject identification numbers that are assigned will not be reused even if the subject does not undergo imaging.

Subjects who withdraw from the study before completing Day 15 and Day 90 PET MRI scans may be replaced by discretion of the principal-investigator .

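### Does the unmarked Screening cell for the NIHSS, or an appended NIHSS form that sums to 44 rather than 42, call for a change to the plan?

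*Combined protocol and SAP*

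**What the plan says.** Criterion 4 in Section 8.1 reads "Score of at least 5 points on the NIHSS at Screening", and the lead-in to that list sets screening as the time at which inclusion criteria apply. The Synopsis repeats the threshold as "moderate severity as measured by NIHSS >4 and evidence" of infarction on the clinical scan. On an integer scale, above 4 and at least 5 are the same cut-off.

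In the Schedule of Events the NIHSS row is blank at Screening and marked at Day 15 and Day 90. The Screening column does carry an eligibility confirmation row, whose footnote 1 says "All but genotype exclusion criterion, see bullet point 8", and a physical and neurological examination row. Footnote 9 times Screening as "Up to 10 days from stroke onset". Footnote 5 adds, for the blood tests only, "Results of tests performed as part of standard of care can be accepted".

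Section 9 states that "subjects may be enrolled if they have met the inclusion criteria in Section 8.1" (and no exclusion applies). Section 9.1 states that "Subjects will be registered at screening visit after the eligibility criteria, with the exception of the TSPO genotype, have been determined".

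Section 10.2 (Clinical Assessments) introduces the scored tools in connection with the PET and MRI days. It describes the NIHSS as having 15 items and a top score of 42, and requires raters to be certified. The Appendix reproduces an NIHSS form, also headed with a maximum of 42, that includes a pupillary response item.

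**The concern.** An entry criterion that depends on a scored scale would normally have its own mark in the visit schedule. Here the cell is empty, and Section 10.2 mentions only a neurological examination after consent. No rule says whether an admission or ward NIHSS may serve, although such a rule is given for blood tests. Screening can fall on any day up to day 10 and rescreening is not allowed, so the choice of score could decide entry. The analysis population in Section 12.2 is limited to eligible subjects, so an undocumented entry score would leave membership of that population hard to verify. It would also lose a severity measure taken before the first scan.

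The form raises a different worry. If raters used it as printed, totals would not lie on the 42-point scale that the protocol describes. A patient just below the threshold could be admitted on pupillary points, and the NIHSS values used in the correlations would shift.

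**Working it through.** **The Screening score.** The relevant statements, side by side:

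| Place | What it settles |
|---|---|
| Section 8.1, lead-in and criterion 4 | The score must be at least 5, at Screening |
| Section 4, eligibility row and footnote 1 | All criteria but genotype are confirmed at Screening |
| Section 4, examination row | A neurological examination takes place at Screening |
| Section 9.1 | Registration follows that determination |
| Section 4, NIHSS row | NIHSS marked at Day 15 and Day 90 only |
| Section 6.1, endpoints | Correlations with severity and functional outcome are set at day 15 and day 90 |

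The first four rows cannot be satisfied unless someone has obtained an NIHSS at Screening. The last two fit a reading in which the NIHSS row lists outcome assessments and the eligibility row covers entry checks. Other entry checks, such as review of the acute CT or MRI and prior radiation exposure, also have no row of their own.

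Interval from Screening (day 0 to 10) to the first scheduled NIHSS:

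- Window of ±3 days in Sections 4 and 6.1 (day 12 to 18): 12 − 10 = 2 to 18 − 0 = 18 days.
- Synopsis wording "in the subacute (day 15+7) and chronic (day 90+/-7) phases after an ischemic stroke", read literally as one-sided (day 15 to 22): 15 − 10 = 5 to 22 − 0 = 22 days.
- The same wording read as ±7 (day 8 to 22): 8 − 10 = −2 to 22 − 0 = 22 days.

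All three ranges follow from the visit windows and would be identical if the Screening cell were marked, so they do not measure any effect of the blank cell. The mismatch of 7 against 3 days is a separate inconsistency to be reconciled on its own account.

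**The appended form.** Top score per item, with arms and legs scored on each side:

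- Left column: consciousness 3 + questions 2 + commands 2 + pupils 2 + gaze 2 + visual fields 3 + dysarthria 2 = 16, over 7 lines.
- Right column: arms 2 × 4 = 8 + legs 2 × 4 = 8 + ataxia 2 + sensory 2 + language 3 + face 3 + extinction 2 = 28, over 9 lines.
- Total: 16 + 28 = 44 over 7 + 9 = 16 lines. The stated 42 is not reproduced.
- Counting each limb item once: 44 − 4 − 4 = 36, also not 42.
- Without the pupillary item: 44 − 2 = 42 over 16 − 1 = 15 lines, matching Section 10.2 on both counts.

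Eight lines have a maximum of 2, so dropping any one of them would give 42 over 15. Pupils is the only one of the eight with no counterpart in the Section 10.2 list of domains. Facial palsy is not named there either, but it scores 3, and dropping it would give 41.

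**Largest effect if the form were used as printed.** The pupillary item adds 0, 1 or 2 points. Against the threshold of 5:

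- 15-item score of 4: 4 + 1 = 5 and 4 + 2 = 6, so entry changes.
- 15-item score of 3: 3 + 2 = 5 changes entry, but 3 + 1 = 4 does not.
- 15-item score of 2 or less: at most 2 + 2 = 4, no change.

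The Day 15 and Day 90 totals could likewise each carry 0 to 2 extra points. The documents give no frequency for abnormal pupils.

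**The case for a change.** The strongest argument for a change is that an implied score is not a specified one. The Schedule gives separate Screening rows to other eligibility inputs, such as the pregnancy test and the genotyping sample, and states a source rule for blood tests. The NIHSS has neither. MoCA is named in the objectives and described in Section 10.2 but has no Schedule row at all, which points to oversight and not to a deliberate umbrella row. Recruitment ends at 15 completers, so losing a pre-scan severity score would be an avoidable waste. The assessment takes about 10 minutes and is needed for entry anyway, so marking the cell adds no burden. The form contradicts its own heading, which nobody can defend.

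Much of this stands as description. The blank cell is probably an oversight, and the form is wrong as printed. What does not follow is a consequence for the study. Criterion 4 names the time, so the score that counts is the one at Screening. Eligibility confirmation is itself a scheduled entry at that visit, so there is a place where the criterion is checked. The case report form is not among the documents and may hold the score and its date. The Synopsis does not clearly offer a rival time: its reference to the time of stroke may apply only to the scan.

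**Conclusion.** No change follows. The unmarked cell is a gap that the site fills in the ordinary course of confirming eligibility, and the surplus pupillary line is a clerical slip in an appendix. The sample size is set on feasibility (Section 12.1), and no endpoint names a Screening NIHSS, so no figure or planned comparison depends on either point.

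The size is nil for the Schedule cell. For the form it is 2 points on the stated maximum (44 against 42) and at most 0 to 2 points on any one total, with entry affected only at 15-item scores of 3 or 4 with abnormal pupils.

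This rests on two assumptions. The first is that the eligibility record shows the score behind criterion 4, as Sections 4 and 9.1 imply. The second is that certified raters score the 15-item scale described in Section 10.2 and do not take totals from the printed form; if they did, the Day 15 and Day 90 correlations could be touched as well as entry.

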9. STUDY PROCEDURES

Once the investigational site has been activated for study participation, subjects may be enrolled if they have met the inclusion criteria in Section 8.1 and have not been excluded based on the exclusion criteria in Section 8.2.

9.1. Screening, Enrollment and Registration of Subjects

Subjects must provide informed consent before any screening tests or assessments are performed. When the subject signs the Informed Consent Form (ICF), the subject is considered to be enrolled in the study. Subjects will not be eligible for rescreening.

Subjects will be registered at screening visit after the eligibility criteria, with the exception of the TSPO genotype, have been determined.

Subjects will be registered and assigned a unique subject identification number after consent and before undergoing imaging acquisition. Any subject identification numbers that are assigned will not be reused even if the subject does not undergo imaging.

Subjects who withdraw from the study before completing Day 15 and Day 90 PET MRI scans may be replaced by discretion of the principal-investigator .

9.2. Follow-up

Subjects will be followed during a 90-day evaluation period during which time each participant is expected to undergo two visits where clinical assessment, blood sampling and PET-MRI scans will be conducted. Subjects will be called by study staff within 7 days after the 90 day study visit including the PET scan to inquire for potential adverse effects.

Withdrawal of Subjects from the Study

Subjects must be withdrawn from the study for any one of the following reasons:

- The subject withdraws consent.
- The subject is unwilling or unable to comply with the protocol.
- The Physician withdraws the subject from the study for medical reasons.

The reason for the subject's withdrawal from the study should be recorded in the subject's case report form (CRF) if provided by the subject.

Participants who lose the capacity to consent during the trial will be withdrawn and have no further study procedures. The study team will retain the data and blood samples that are collected up until that point but no new data on the participant will be recorded.

10. DATA COLLECTION

10.1. Imaging Assessments

PET and MRI

10.1.1 Positron Emission Tomography (PET)

PET imaging involves the estimation of the availability of a specific molecular target via the evaluation of the tissue kinetics of a specific molecule administered at tracer amounts and labelled with a positron emitting radionuclide. PET imaging allows the accurate estimation of the availability of the molecular target of interest before and after an intervention or over time. Each PET scan session in this study, will include the administration of [11C]PBR28, a PET radioligand suitable for the quantification of TSPO availability in the human brain.

10.1.2 Magnetic Resonance Imaging (MRI)

MRI involves the use of an intense magnetic field to quantify tissue anatomical characteristics. In this study MRI will be used to define the volume of the stroke affected areas, and physiological characteristics of the brain tissue relevant to stroke physiology. In addition, a Gadolinium conjugated contrast agent will be used to assess the regional integrity (i.e. permeability) of the blood-brain-barrier. Each MRI scanning session will be up to 90 min in duration and will include the administration of a Gadolinium-conjugated contrast agent.

10.2 Summary of Risk Management for Imaging

10.2.1 [11C]PBR28

10.2.1.1 Pre-clinical safety and toxicology

Safety and toxicity of PBR28 was studied in rodents and healthy human volunteers (n=10), at the National Institutes of Health (NIMH), USA. (National Institute of Health.html> February 2011). In an i.v. toxicity study in male and female Sprague-Dawley rats the NOAEL dose was determined to

be 445 µg/kg for a single dose, and 88µg/kg for repeat dose administration.

10.2.1.2 Clinical Safety

In humans, pharmacological effects of [11 C]PBR28 were monitored by performing vital signs and ECG monitoring, as well as blood tests (including full blood count, electrolytes, liver enzymes, creatinine) and standard urinalysis following i.v. injection of doses $\leq 10 \mu g$. No subject showed clinically

significant changes in vital signs after administration of [¹¹C]PBR28. Two subjects showed minor changes in laboratory tests, which could not be linked to administration of [¹¹C]PBR28 (Tracer Database Initiative).

